### 6.6.1.3 Serious Adverse Events and other Events

SAEs, MAAEs, AEs leading to withdrawal of vaccine and AEs leading to study discontinuation will be summarized in the same manner as unsolicited AEs:

- Overview table
- Events by SAE criteria (only applicable for SAEs)
- Summary by SOC and PT
- Summary by PT
- Summary by SOC, PT and Severity
- Summary of related events by SOC and PT
- Summary of related events by SOC, PT and severity

SAEs with fatal outcome will be summarized by SOC and PT.

SAEs, MAAEs, AE leading to discontinuation and AEs with fatal outcome will be summarized for the following analysis sets and time intervals:

Analysis set	Time interval
Phase 1/2/3a SAS	

• From Day 1 to Day 92 (for participants without Switchover/Further study vaccine) or Switchover/Further study vaccine . Percentages will be computed based on the number of participants in SAS who received at least one dose of study vaccine during reporting period (i.e a dose at Day 1 or at Day 29).

• From Switchover/Further study vaccine to End of study, for participants with Switchover/Further study vaccine. Percentages will be computed based on the number of participants in SAS who received at least one dose of study vaccine during reporting period (i.e a dose at Day 92 or at Day 120).

• From Day 92 to End of Study, for participants without Switchover/Further study vaccine. Percentages will be computed based on the number of participants in SAS still on study at Day 92 and without Switchover or further study vaccine.

• From the first dose of ARCT-154 vaccine administration to End of Study. Percentages will be computed based on the number of participants in SAS who received at least one dose of ACRT154 study vaccine.

Phase 3b SAS	
Phase 3c SAS	

• From Day 1 to Day 92. Percentages will be computed based on the number of participants included in Phase 3c SAS.

---

	

• From Day 92 to End of Study. Percentages will be computed based on the number of participants included in Phase 3c SAS.

Pooled SAS	From Day 1 to Day 92 (for participants without Switchover/Further study vaccine) or Switchover/Further study vaccine (main estimation). Percentages will be computed based on the number of participants in Pooled SAS who received at least one dose of study vaccine during reporting period (i.e Day 1 or Day 29).

---

Overview table and output by SOC and PT for SAEs from the first dose of ARCT-154 vaccine administration to End of Study for Phase 3b SAS will be also produced by subgroups as specified in Section 6.2.5.

The following participant data listings will be produced using the randomized set:

- SAEs
- MAAEs
- AEs leading to premature discontinuation of vaccine series
- AEs leading to withdrawal from the study
- AEs with Fatal Outcome

A separate set of listings will be produced for these AEs occurring in the set of participants who received at least one incorrect dose of study vaccines.

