5.1.5 Swithcover/Further Study Vaccine Eligibility Criteria

At Day 92, all participants in Phase 1, 2, 3a and 3b will be reviewed for eligibility to receive further study vaccine based on meeting any of the following exclusionary criteria on Day 92. Participants meeting any of the following criteria will be excluded from receiving further study vaccine administration:

- Significant infection or other acute illness, including body temperature $>100.4^{\circ}\text{F}$ ($>38.0^{\circ}\text{C}$) on the day prior to or day of planned Swithcover/Further Study Vaccine vaccine administration (see Section [5.2.1](#)).
- Pregnant or breastfeeding.
- Persistence of symptoms from COVID-19 disease (recovered COVID-19, asymptomatic SARS-CoV-2 infection and/or nucleocapsid positive test is not exclusionary).
- Receipt of an off-study COVID-19 vaccine since study enrollment.
- Demonstrated inability to comply with the study procedures since study enrollment.
- Development of new severe allergy to vaccine components since study enrollment. See the IB for list of vaccine components.
- New onset of bleeding disorder considered a contraindication to IM injection or phlebotomy.
- New onset of immunosuppressive or immunodeficient state, asplenia, or recurrent severe infections.
- Has received a live replicating vaccine within 28 days prior to intended Swithcover/Further Study Vaccine vaccine administration or an inactivated or non-replicating vaccine within 14 days prior to intended Swithcover/Further Study Vaccine vaccine administration. Please see Section [5.2.1](#) for guidance on deferral of study vaccination.

- Has received immunosuppressive therapy, including cytotoxic agents or has initiated systemic corticosteroid therapy. If systemic corticosteroids have been administered short term (<14 days) for treatment of an acute illness, see Section 5.2.1 for additional guidance. Inhaled/nebulized, intra-articular, intrabursal, or topical (skin or eyes) corticosteroids are permitted.
- Has received systemic immunoglobulins or blood products within the past 3 months.
- Has newly identified that they are investigator site staff members, employees of the Sponsor or the CRO directly involved in the conduct of the study, or site staff members otherwise supervised by the investigator or immediate family members of any of the previously mentioned individuals.

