7.4.1.3 Reporting Adverse Events

Non-serious unsolicited AEs are recorded through 28 days after study vaccine administration, unless they meet the protocol definition of MAAE, SAE, or AEs leading to withdrawal/discontinuation, which will be recorded and reported for the duration of study participation.

All unsolicited AEs reported or observed during the study will be recorded on the AE page in the eCRF. Information to be collected includes the following:

- event term
- date of onset
- date of resolution/stabilization
- for AEs occurring within 24 hours of the vaccination only: time of onset
- investigator-specified assessment of severity and relationship to the study vaccine or study procedure
- for AEs initiating and resolving within 24 hours of the vaccination only: time of resolution of the event
- seriousness
- any required treatment or evaluations
- outcome
- whether the AE met the protocol definition of MAAE
- whether the AE led to study vaccine withdrawal

Adverse events resulting from concurrent illnesses, reactions to concurrent illnesses, reactions to concurrent medications, or progression of disease states must also be reported. All AEs (solicited and unsolicited) will be followed to adequate resolution. The Medical Dictionary for Regulatory Activities (MedDRA) dictionary will be used to code all unsolicited AEs.

Any medical condition that is present at the time that the participant is screened but does not deteriorate should be reported as medical history rather than as an AE. However, if this medical condition deteriorates at any time during the study, it should be recorded as an AE.

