#### 6.6.1.2 Unsolicited Adverse Events

Unsolicited AEs are defined as any spontaneously reported or discovered AE. Unsolicited AEs can also be solicited AE that leads to: A medically attended visit, an SAE, a discontinuation of study vaccine, a withdrawal from the study, or any solicited AE that persists beyond 7 days after the first study vaccine administration.

Unsolicited AEs will be coded using the MedDRA and displayed in tables using System/Organ/Class (SOC) and Preferred Term (PT). Treatment emergent AEs will be presented in tables, and all AEs will be included in listings where applicable.

In any tabulation, unsolicited AEs will be summarized by participant, therefore, a participant contributes only once to the count for a given Unsolicited AE (SOC or PT) in the tabulation. All episodes of all events will be provided in listings.

Unsolicited AEs with onset during the first 28 days after vaccination will be analyzed in the following analysis sets as defined below:

Analysis set	Timepoint
Phase 1/2/3a SAS	

After Dose 1, after Dose 2, after Dose 1 or 2

After Dose 3, after Dose 4

After Any dose

Phase 3b SAS	

After Dose 1, after Dose 2, after Dose 1 or 2

After Dose 3, after Dose 4

After Any dose

Phase 3c SAS	

After Dose 1, after Dose 2, after Dose 1 or 2

	• After Any dose
Pooled SAS	• After Dose 1, after Dose 2, after Dose 1 or 2
	• After Dose 3, after Dose 4
	• After Any dose

Participants will be considered for the computation of percentages in the specified time interval if they received the study vaccine in the specified interval. For each time interval the number of participants without missing dose will be presented.

Only data up to receipt of non-study COVID-19 vaccine (IcEv2) will be included in summary tables. Participant's data after the receipt of non-study COVID-19 vaccine will be summarized separately in a similar manner as unsolicited AEs for the following time interval: from the receipt of non-study COVID-19 vaccine up to the Final Visit/ET.

The following summaries will be presented for unsolicited AEs:

- Overview of number and percentage of participants with at least one:
  - AE
  - Related AE
  - AE by severity
  - MAAE
  - Related MAAE
  - SAE
  - Related SAE
  - AE leading to premature discontinuation of vaccine series

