	antinucleocapsid antibody or neutralizing antibody (as assessed by sVNT for Phase 1/2/3a and MNT for Phase 3c) indicating exposure to SARS-CoV-2 prior to vaccination or SARS-CoV-2 infection prior to 7 days (inclusive) after the second study vaccination dose (Day 35).	other COVID-19 positive test or seropositivity for anti-nucleocapsid antibody indicating exposure to SARS-CoV-2 prior to vaccination or SARS-CoV-2 infection prior to 7 days (inclusive) after the second study vaccination dose (Day 35).  Note: This also impacts mITT and IAS analysis sets definitions where IcEv3 is considered.	assessment of early infection
Section 8.3.1 Table 15 (estimand 1 – Rationale for Strategies)	IcEv4 and IcEv5 could also be potentially confounding but it is more difficult to determine the precise timing of these events, so a principal stratum strategy is used to exclude these participants from immunogenicity analyses.	IcEv4 and IcEv3 could also be potentially confounding but it is more difficult to determine the precise timing of these events, so a principal stratum strategy is used to exclude these participants from immunogenicity analyses.	Correction
Section 8.3.1 Table 17 (estimand 3 – unsolicited Aes - Intercurrent Event (IcEv) Strategy)	Intercurrent Event (IcEv) Strategy:  IcEv2 (Non-study vaccine): treatment policy strategy  IcEv5 (Confounding On-study Medications): composite strategy	IcEv2 (Non-study vaccine): while on treatment strategy  IcEv5 (Confounding On-study Medications): treatment policy strategy	IcEv2: Correction of the name of the strategy to reflect the fact that events occurring after IcEv2 will not be included in the analysis as specified in protocol  IcEv5: Correction of the name of the strategy to reflect the fact that events occurring after IcEv5 are included in the analysis as specified in the protocol
Section 8.3.1 Table 17 (estimand 4 – Reactogenicity - Rationale for Strategies)	Events occurring after IcEv2, IcEv3 and IcEv5 could contribute spurious reactogenicity data so a treatment policy is used for these events and events occurring after	All solicited events will be analyzed regardless of occurrence of intercurrent events.	Reactogenicity is participant reported outcome, which will be analyzed as it is without modification.

	these IcEv's will be summarized separately		

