### 9.2.3 Estimands for Primary Safety Analyses for Phase 1/2/3a, Phase 3b, Phase 3c and Pooled Cohorts

Estimand Label	Estimand 3 (Safety – Unsolicited AEs/AEs leading to discontinuation or withdrawal/MAAE/SAE)
Estimand Description	
Count and percentage of vaccinated participants who would develop unsolicited AEs, AEs leading to discontinuation/withdrawal, MAAEs, and SAEs.
 
These will be evaluated with each dose of study vaccine, ARCT-154 or placebo.

Target Population	The population who are enrolled in the study and receive any dose of study vaccine

Endpoint	Occurrence of unsolicited AEs will be analyzed up to 28 days after each study vaccine administration.  Occurrence of AEs leading to discontinuation/withdrawal, MAAEs, or SAEs will be analyzed up to Day of Switchover/Further Study Vaccine, receipt of non-study vaccine, early withdrawal, or last on-study assessment visit, whichever comes first.  Occurrence of AEs leading to discontinuation/withdrawal, MAAEs and SAEs after the Switchover/Further Study Vaccine will be recorded and summarized for the interval from the switchover/Further Study Vaccine up to Day 394 (Phase 1/2/3a and Phase 3b only).  For Phase 1/2/3a and 3b, AEs in participants who do not undergo Switchover/Further Study Vaccine will be recorded for the interval from Day 92 up to Day 394
Treatment Conditions	Phase 1/2/3a and 3b: ARCT-154 dose 5 µg or placebo administered on Day 1, Day 29, or at Switchover/Further Study Vaccine (Day 92 and Day 120)  Phase 3c: ARCT-154 dose 5 µg or ChAdOx1 administered on Day 1 and Day 29.
Population-Level Summary	Percentage of vaccinated participants who develop each type of AE
Intercurrent Event (IcEv) Strategy	
IcEv1 (Death not due to COVID-19)	Composite strategy
IcEv2 (Non-study vaccine)	While on treatment strategy
IcEv3 (Early infection)	Composite strategy

IcEv4 (Study infection)	Composite strategy
IcEv5 (Confounding On-study Medications)	treatment policy strategy
Rationale for Strategies	Events occurring after IcEv2 could contribute spurious safety data so a while on treatment policy is used for these events and events occurring after this IcEv's will be summarized separately.
Estimand Label	Estimand 4 (Reactogenicity – Solicited AEs)
Estimand Description	Count and percentage of vaccinated participants who would develop solicited AEs. These will be evaluated after vaccination on Day 1 and Day 29, ARCT-154 or placebo.

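### SAE, MAAE and discontinuation percentages after Day 92 use headcounts that ignore the cut at non-study COVID-19 vaccination, which dilutes the row for participants without Switchover

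*SAP*

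**What the plan says.** **Which events count.** SAP 6.6.1.2 says of unsolicited AEs: "Only data up to receipt of non-study COVID-19 vaccine (IcEv2) will be included in summary tables". Later data go to a separate summary that runs from the non-study vaccination to the Final Visit or early termination. SAP 6.6.1.3 then says: "SAEs, MAAEs, AEs leading to withdrawal of vaccine and AEs leading to study discontinuation will be summarized in the same manner as unsolicited AEs". Estimand 3 in SAP 9.2.3 covers all of these event types and gives non-study vaccination (IcEv2) a while-on-treatment strategy. SAP 7.1 explains that label by noting that "events occurring after IcEv2 will not be included in the analysis as specified in protocol".

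**Who is divided by.** Every denominator in SAP 6.6.1.3 is a headcount:
- Day 92 to End of Study, for those who were given no later dose, follows this rule: "Percentages will be computed based on the number of participants in SAS still on study at Day 92 and without Switchover or further study vaccine".
- Switchover or further study vaccine to End of Study: those dosed at Day 92 or Day 120.
- First ARCT-154 dose to End of Study: everyone with at least one ARCT-154 dose.
- Phase 3c, Day 92 to End of Study: the whole Phase 3c Safety Analysis Set.

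None of these excludes participants with IcEv2, and none uses person-time.

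**Who lands in the row without Switchover.** Protocol 5.1.5 lists among the reasons for receiving no further study vaccine: "Receipt of an off-study COVID-19 vaccine since study enrollment". Protocol 5.2.3 and 6.8.1 ask such participants to stay in the study to Day 394.

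**The concern.** The numerator stops at non-study vaccination and the denominator does not. In the row without Switchover this is more than lost precision. Off-study vaccination before Day 92 is itself a reason for being in the row, and those participants are asked to remain, so they meet the on-study condition. Their countable time ended before the interval began. They are in the denominator and cannot appear in the numerator.

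The other rows that run to End of Study lose only part of each vaccinated participant's time. The percentage is still a proportion of people with an event before non-study vaccination, but its label suggests follow-up to the end of the study. Rows with different off-study uptake then differ in exposure without the table showing it. In Phase 3c, the row from Day 92 also divides by people who left before Day 92.

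At stake is how late SAE and MAAE rates are read: part of a low figure could come from the denominator.

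**Working it through.** The documents state no figure for this point, so there is nothing to reproduce.

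**Inputs**
- Interval: Day 92 to Day 394 = 394 - 92 = 302 days.
- v = share of the row vaccinated off study before Day 92; w = share vaccinated off study after Day 92. Neither is in the documents, so 10% to 90% is shown.
- True event risk over 302 days: assumed 2.0% with constant hazard h = -ln(0.98)/302 per day, which is 2.44 events per 100 person-years. The relative shortfall hardly depends on this choice.

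**Formula.** Reported % = sum over participants of [1 - exp(-h × t)] / headcount, where t is the number of days from Day 92 to the earlier of non-study vaccination and Day 394.

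**Row without Switchover.** Someone vaccinated before Day 92 has t = 0 and still counts as one person. With no later vaccination, reported = (1 - v) × true.

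**Switchover row.** Participants must be free of non-study vaccine at Day 92. If vaccination is uniform over the 302 days, a vaccinated participant keeps half the interval on average, so reported is about (1 - w/2) × true.

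| v or w | Without Switchover, share v before Day 92 | Switchover, share w uniform after Day 92 |
|---|---|---|
| 10% | 1.8% | 1.90% |
| 25% | 1.5% | 1.75% |
| 50% | 1.0% | 1.50% |
| 75% | 0.5% | 1.25% |
| 90% | 0.2% | 1.10% |

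At equal shares the relative shortfall is v in the first row and about half that in the second. Uniform timing is an assumption. A participant vaccinated 28 days after the Day 120 dose, on Day 148, loses 394 - 148 = 246 of 302 days, or 81%.

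**Phase 3c, Day 92 to End of Study.** If share d left before Day 92, the denominator alone scales the percentage by 1 - d. Protocol 8.5.3 plans for 20-25% dropout in the Phase 3c-1 immunogenicity sample. Borrowed here purely as an illustration, it gives factors of 0.80 to 0.75. Non-study vaccination before Day 92 would lower the figure further.

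**Check of the remedy.** Events divided by person-time ending at non-study vaccination:
- v = 50%, w = 0: 0.010 / (0.50 × 302/365.25) = 2.42 per 100 person-years (headcount 1.0%).
- v = 0, w = 50%: 0.01502 / (0.75 × 302/365.25) = 2.42 (headcount 1.5%).
- v = 50%, w = 25%: also 2.42 (headcount 0.75%).

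The small gap to 2.44 arises because person-time here is not stopped at the first event. Removing participants vaccinated before Day 92 from the denominator restores 2.0% in the first case. Vaccination after Day 92 still needs person-time.

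**The case against.** **The cut after Day 92 is inferred.** In SAP 6.6.1.3 the same-manner sentence introduces a list of table layouts. SAP Table 8 names non-study vaccine as a stop only for the interval up to Day 92. In Estimand 3 the stop at "receipt of non-study vaccine, early withdrawal, or last on-study assessment visit, whichever comes first" sits in the sentence on the period before Switchover, and the sentences on later intervals do not repeat it. This stands as a call for clearer wording. It does not remove the point, because 6.6.1.2 limits the summary tables without restriction to a period and moves everything up to the Final Visit elsewhere, and the while-on-treatment strategy covers all of Estimand 3.

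**A while-on-treatment proportion is legitimate.** This stands for the rows where people start at risk: they are low only against the interval on the label. It does not rescue the row without Switchover, where some of the people counted have no time at risk at all.

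**Events are not lost.** Correct. SAP 6.6.1.2 summarises them separately, and 6.6.1.3 lists SAEs, MAAEs, discontinuation AEs and fatal AEs for the randomized set. However, no dedicated denominator for that summary is stated. SAP 7.2 also drops the ITT sensitivity analysis that Protocol Table 17 planned to include such events.

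**Stronger readings that do not hold.**
- A reader might take the row without Switchover for a control group. It is self-selected from both initial arms for any reason in Protocol 5.1.5, so comparing it with the Switchover row would be unsound even with perfect denominators.
- A reader might infer that off-study uptake was large because SAP 7.1 drops Day 394 titres over routine vaccination. That entry gives no share.
- A reader might call the row without Switchover the worst affected overall. That cannot be shown against the Phase 3c row.
- A reader might expect non-serious AEs after an off-study vaccine to be almost unrecorded, since Protocol 7.4.1.3 says "Non-serious unsolicited AEs are recorded through 28 days after study vaccine administration". Protocol 4.5.5.2 has unsolicited AEs recorded through the Final Visit, and the 28-day spacing before off-study vaccine in Protocol 5.2.3 is only a preference.

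**Conclusion.** The point holds for the denominators. As written, the percentage in the row without Switchover is diluted by exactly the share v vaccinated off study before Day 92. The other rows to End of Study carry shortened, unequal follow-up under a label that does not say so, with about w/2 lost if vaccination is spread evenly. The Phase 3c row from Day 92 also counts people no longer in the study.

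The direction follows from the text. The size does not, because the documents give neither counts nor dates of non-study vaccination; the figures are illustrations that assume a constant hazard, equal risk across participants and, for w, uniform timing.

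The consequence is limited to descriptive rates. There is no hypothesis test on safety (SAP 6.2.3), and for Phase 1/2/3a and 3b safety analyses after the Day 92 analysis are exploratory (Protocol 8.9.1 and 8.9.2). Phase 3c differs in that its primary safety analysis is at Day 394 (Protocol 8.9.3), so its row from Day 92 deserves the same correction.

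**What to change.** In SAP 6.6.1.3:

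1. Restrict the denominator of the row without Switchover to participants on study at Day 92 with no non-study COVID-19 vaccine before Day 92. Restrict the Phase 3c row from Day 92 to participants on study and still uncensored at Day 92.
2. For every interval ending at End of Study, state that counted follow-up ends at non-study vaccination. Add incidence per 100 person-years, with person-time ending at the earliest of non-study vaccine, withdrawal, death or End of Study.
3. State the N and person-time for the separate summary after non-study vaccination, and keep non-serious AEs in it.

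**Cost.** A few lines of SAP text and one extra column per table. SAP 6.4.1 already computes person-years for efficacy. Late rates will look slightly less favourable.

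**Before programming.** Confirm that non-study vaccination dates are complete. Protocol 6.8.1 records non-study vaccinations, and vaccines used to prevent COVID-19, throughout participation. A later sentence in the same section limits entries beyond 28 days after a dose to those linked to an SAE, MAAE or discontinuation AE. If sites followed the narrower rule, dates would be missing mainly for people without events, and their person-time would be overcounted.

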8.5.3 Sample Size for Phase 3c Substudy

Immunogenicity endpoints will be evaluated in participants in the Phase 3c-1 IAS (Section 8.2). Sensitivity analyses will be performed in the Phase 3c PP set. For the primary immunogenicity noninferiority endpoint of neutralizing antibody (using the pseudovirus microneutralization assay [MNT]) geometric mean ratio (GMR), assuming a GMR of ≥ 0.9 and a coefficient of variation of variation of 4.6, a sample size of 800 participants in Phase 3c-1 will provide greater than 90% power to exclude a non-inferiority boundary of 0.67 based on the use of a one-sided test at the alpha=0.025 level of significance, accounting for a dropout rate of approximately 20-25% due to the national COVID-19 vaccination campaign in Vietnam.

The primary safety endpoints of Phase 3c will be conducted in the Phase 3c Safety Analysis Set and Phase 3c Reactogenicity Analysis Set (Section 8.2). With a sample size of approximately 2,400 participants randomized and with approximately 1,200 participants randomized in the study to receive ARCT-154 or ChAdOx1 for the safety analysis, based upon the following formula, if the incidence rate of an adverse event is 0.1%, the probability to detect one event in 1,200 vaccinated participants is 69.9% and if the incidence rate is 1.0% the probability is more than 99%:

$$p = 1 - (1 - R)^N$$

where R = incidence rate and N = sample size

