- **Safety Analysis Set (SAS):** Includes all participants who receive any dose of study vaccine (ARCT-154 or placebo or ChAdOx1). Participants will be analyzed according to the study vaccine received. SAS analysis sets are defined for each Phase of the study as follows:
  - Phase 1/2/3a SAS: this pools data from Phase 1, Phase 2 and Phase 3a participants
  - Phase 3b SAS
  - Phase 3c SAS
  - Pooled SAS: this pools data from Phase 1/2/3a/3b for ARCT-154 and placebo, respectively. It will include evaluations up to Day 92 only (except for unsolicited events)
- **Reactogenicity Analysis Set (RAS):** Includes all participants who receive any dose of study vaccine (ARCT-154 or placebo or ChAdOx1) and provide at least 1 reactogenicity diary report. Participants will be analyzed according to the vaccine received.  
Reactogenicity analysis sets are defined for each Phase of the study as follows:
  - Phase 1/2/3a RAS: this pools data from Phase 1, Phase 2 and Phase 3a participants
  - Phase 2/3a RAS
  - Phase 3b RAS
  - Phase 3c RAS
  - Pooled RAS: this pools data from Phase 1/2/3a/3b for ARCT-154 and placebo, respectively.

For safety analysis sets, SAS and RAS, where participants will be analyzed according to the study vaccine received, in case a participant receives incorrect study vaccine, only data up to the receipt of the incorrect study vaccine (exclusive) will be used in the summaries. If the first dose of vaccine the participant received was the incorrectly assigned one, then only data up to the second dose (exclusive) will be used in the summaries. Outputs for “any dose” that analyze data after any ARCT-154 dose or after any Placebo or ChAdOx1 dose, will include all data after each dose even if participant received an incorrect study vaccine.

Separate listings of safety and immunogenicity data, that are currently planned in this SAP, will be produced for participants receiving at least one incorrect dose of study vaccine. Of note, participants with missing dosing will not be considered as receiving incorrect dosing.

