### Sample Size for Phase 3c Substudy

The primary safety endpoints of Phase 3c will be conducted in the Phase 3c Safety Analysis Set and Phase 3c Reactogenicity Analysis Set. With a sample size of approximately 2,400 participants randomized and with approximately 1,200 participants randomized in the study to receive ARCT-154 or ChAdOx1 for the safety analysis, based upon the following formula, if the incidence rate of an adverse event is 0.1%, the probability to detect one event in 1,200 vaccinated participants is 69.9% and if the incidence rate is 1.0% the probability is more than 99%:

$$p = 1 - (1 - R)^N$$

where R = incidence rate and N = sample size

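### Phase 3c safety percentages for Day 92 to End of Study are divided by everyone ever dosed, including people who left before the window opened, so late event rates are never overstated and usually understated

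*SAP*

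**What the plan says.** The table in SAP 6.6.1.3 gives Phase 3c two windows. The first runs from Day 1 to Day 92 on the Phase 3c SAS. The second is "From Day 92 to End of Study. Percentages will be computed based on the number of participants included in Phase 3c SAS". SAP 4.1 defines the SAS by dosing alone: "Includes all participants who receive any dose of study vaccine (ARCT-154 or placebo or ChAdOx1". It sets no follow-up condition.

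For Phase 1/2/3a, the same table ties the denominator to presence at the start of each later window:

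- Day 92 to End of Study, when no Switchover or further vaccine is given: "Percentages will be computed based on the number of participants in SAS still on study at Day 92 and without Switchover or further study vaccine".
- Switchover or further vaccine to End of Study: SAS participants "who received at least one dose of study vaccine during reporting period (i.e a dose at Day 92 or at Day 120".

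The Phase 3b cell is empty in the text we have and appears to be merged with the Phase 1/2/3a cell. The sentence after the table supports this, because it uses one of those windows for the Phase 3b SAS. The Pooled SAS has no window after Day 92.

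SAP 6.6.1.3 says these events are summarised in the same way as unsolicited AEs. For those, SAP 6.6.1.2 states: "Only data up to receipt of non-study COVID-19 vaccine (IcEv2) will be included in summary tables". Later events are summarised separately. Estimand 3 in SAP 9.2.3 covers SAEs and MAAEs and handles a non-study vaccine with a while-on-treatment strategy, which agrees.

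SAP 7.1 explains the choice of windows only as avoiding overlapping periods. It gives no reason for a different Phase 3c denominator.

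**The concern.** A percentage for a time window should divide events in the window by people who entered it. In Phase 3c, someone lost at Day 40 is counted for Day 92 to End of Study but cannot add an event. The effect goes one way: late percentages are never too high, and they are too low as soon as one SAS member leaves before Day 92.

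Safety against ChAdOx1 is a Phase 3c primary objective. Protocol 8.9.3 places the primary Phase 3c safety analysis after Day 394. SAP 7.1 drops the Phase 3c immunogenicity and efficacy analyses, so safety is all that remains of this substudy. The late window spans 394 − 92 = 302 of the 394 days. Similarly labelled windows in the other phases would also rest on a different kind of denominator.

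**Working it through.** **Inputs**

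- Phase 3c arm size: "approximately 1,200 participants randomized in the study to receive ARCT-154 or ChAdOx1 for the safety analysis" (SAP 6.1).
- Late-window denominator: the full Phase 3c SAS (SAP 6.6.1.3).
- d, the share of an arm's SAS no longer on study at Day 92: not given in either document. A range of 2% to 25% is assumed.

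**The plan's own figure.** The only numerical Phase 3c safety statement is the chance of seeing at least one event. With R = 0.001 and N = 1,200, 1 − (1 − 0.001)^1200 = 0.699, which matches the stated 69.9%. It says nothing about the late window.

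**Effect of the denominator.** Let E be the number of participants with a late event and N the SAS size.

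- Displayed percentage = E / N
- On-study percentage = E / [N(1 − d)]
- Displayed / on-study = 1 − d

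With N = 1,200 per arm:

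| Assumed d | On study at Day 92 | On-study risk of 2.0% is displayed as | 12 participants with an event: SAS basis | Same 12: on-study basis |
|---|---|---|---|---|
| 2% | 1,176 | 1.96% | 1.00% | 1.02% |
| 5% | 1,140 | 1.90% | 1.00% | 1.05% |
| 10% | 1,080 | 1.80% | 1.00% | 1.11% |
| 20% | 960 | 1.60% | 1.00% | 1.25% |
| 25% | 900 | 1.50% | 1.00% | 1.33% |

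**Between arms.** With equal on-study risks, the displayed ratio is (1 − d in one arm) / (1 − d in the other). Equal d gives 1. With 20% against 25% it is 0.80 / 0.75 = 1.07, or 0.75 / 0.80 = 0.94 the other way round.

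**Non-study vaccine, a separate mechanism.** Let v be the share of the SAS still on study at Day 92 but already vaccinated off-study. Their later events leave the main table, yet they remain in the denominator, so the factor becomes 1 − d − v. As an illustration only, d = 5% and v = 10% give 0.85, and 2.0% would be displayed as 1.70%. An on-study rule alone does not remove this group.

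The Phase 1/2/3a and 3b Day 92 window has the same gap. Protocol 5.1.5 bars recipients of a non-study vaccine from Switchover or further doses, and Protocol 6.8.1 asks them to stay in the study. They therefore fall into exactly the group that is on study without Switchover.

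**The case against.** The best defence is Estimand 3. Its population is everyone enrolled and dosed, and its summary is a percentage of vaccinated participants, which is the SAS. Keeping everyone also preserves the randomised groups, whereas an on-study denominator conditions on something that happens after randomisation. This stands as a reason to keep a full-SAS column. It does not explain why the same estimand, applied to the other phases in the same table, yields an on-study denominator.

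It can also be said that the other phases' restriction comes from splitting people by Switchover, which Phase 3c lacks, and that their window from the first ARCT-154 dose uses everyone dosed. The split explains the condition about Switchover but not the one about being on study at Day 92. The first-dose window opens at that dose, so everyone in its denominator does enter it.

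The impact is limited. SAP 6.2.3 has no hypothesis test for Phase 3c safety, and SAP 7.2 drops confidence intervals for AE incidence. Counts accompany the percentages. SAP 6.3.1 tabulates disposition separately for Day 1 to 91 and Day 92 onward, so a careful reader can see early losses by arm. Events are listed, and Phase 3c is not in the Pooled SAS. All of this stands, and it makes the matter one of presentation, not inference.

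**Conclusion.** The denominator does not fit the window, and the SAP offers no reason for departing from the rule it uses elsewhere in the same table. The direction is certain. The size is (1 − d), with d unknown: negligible at 2% loss, a tenth of the displayed rate's proper value at 10%, and a fifth to a quarter at 20% to 25%.

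Three stronger readings are tempting, and the documents do not support them.

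- **That late rates are understated by 20% to 25%.** Protocol 8.5.3 does plan its sample size "accounting for a dropout rate of approximately 20-25% due to the national COVID-19 vaccination campaign in Vietnam", but this is an allowance for the Phase 3c-1 immunogenicity comparison at Day 57. Recipients of a non-study vaccine are encouraged to remain in follow-up, so the figure need not mean loss from the study before Day 92. It serves here only as the upper end of an assumed range.
- **That the comparison with ChAdOx1 is biased.** This follows only if losses differ by arm, and nothing in the documents shows that they do.
- **That the other phases already exclude people with an earlier non-study vaccine.** Their rule reads "number of participants in SAS still on study at Day 92 and without Switchover" or further study vaccine, and says nothing about outside vaccines. Excluding such people needs its own justification, which SAP 6.6.1.2 and Estimand 3 supply.

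Nor does the on-study denominator give a true risk, since people who leave soon after Day 92 still count in full.

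**What to change.** For Phase 3c, Day 92 to End of Study, use as denominator the Phase 3c SAS participants still on study at Day 92. If the sponsor wants to keep the full-SAS percentage, show it as a second, clearly labelled column.

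As a separate change, exclude from this window's denominator anyone who received a non-study COVID-19 vaccine before Day 92, because their later data are removed from the main tables. Apply the same condition to the Day 92 window without Switchover in Phase 1/2/3a and 3b. Adding it to Phase 3c alone would create a new inconsistency.

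The cost is a line or two in SAP 6.6.1.3, an entry in SAP 7.1 and a small programming change, with no new data. SAP 2.4 describes Phase 3c as blinded while this SAP was being developed; if that is still so, the rule can be changed without knowledge of the results. The downside is a somewhat smaller denominator, conditioned on retention after randomisation, in a table that is descriptive anyway.
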